## 2 VERSION HISTORY

| Version | Description  | Date      |
|---------|--|-----------|
| 1.0     | Initial Version  | 15Apr2020 |
| 2.0     | 
Version based on Protocol Amendment 02
 
 
- Revised primary objective and efficacy endpoint to progression-free survival (PFS), and changed PFS rate at 4 months (PFS-4m) from primary to secondary objective and endpoint
 
- The primary efficacy endpoint of PFS per IIR will be analyzed by the stratified log-rank test adjusting for the randomization stratification factors of “Age (<18 vs ≥18 years)” and “Time to first relapse/refractory disease (early [<18 months] vs late [≥18 months])”.
 
- Clarify that tumor efficacy endpoint(s) will be based on investigator and IIR evaluations.
 
- Revised sample size calculation based on PFS, with the primary analysis being performed after 38 PFS events occur.
 
- Add objective response rate (ORR) as a secondary endpoint.
 
- Add 2 sensitivity analyses: 1) baseline tumor removal is considered part of the drug therapy, 2) PD or death after two or more missing assessments, or after receiving a new anticancer therapy will be considered as a PFS event.
 
- Clarify exploratory endpoints
 
- Revise the definition of the Randomization Phase to: The Randomization Phase will begin at the time of randomization of the first subject and will end on the data cutoff date for the primary analysis (ie, when approximately 38 PFS events, as determined by IIR, are observed).
 
- Revise the length of follow-up from “will continue as long as the subject is alive” to “will continue for up to 2 years after end of treatment for a subject” unless the subject withdraws consent, or is lost to follow-up, or the sponsor terminates the study.
 
- Added Optional Lenvatinib Crossover Treatment for Subjects in Arm B who experience progressive disease.
 
 | 13Dec2021 |
| 3.0     | 
 
- Updates to handling of subjects with removal of baseline lesions within 1) primary efficacy endpoint, 2) sensitivity analysis 1.
 
- The primary efficacy endpoint of PFS per IIR will be analyzed by the stratified log-rank test with randomization
 
   | 06Jun2022 |

|  |  |  |
|--|--|--|
|  | 
stratification factor of Age (<18 vs ≥18 years). Stratification factor of time to first relapse/refractory disease (early [<18 months] vs late [≥18 months]) is removed due to small subject numbers for stratum ≥ 18 months based on blinded data review.
 

- Addition of subgroup analyses for the primary efficacy endpoint, PFS:

- Age (<18 years, ≥18 years)

- Time to first relapse (<18 months, ≥18 months)

- Sites of metastasis [Lung only, Others (+/- lung)]

- Prior Ifosfamide +/- Etoposide (Yes, No)

- Measurable disease [Yes (Subjects with at least 1 target lesion), No (Subjects with only non-target lesions)]

- Multiple editorial updates

- For DCR, change SD minimum duration period to 5 weeks from 7 weeks after randomization. The change was made due to the tumor assessment schedule of every 6 weeks until Week 18.

 |  |
|--|--|--|

### 3 LIST OF ABBREVIATIONS AND DEFINITIONS OF TERMS

| Abbreviation | Term   |
|--------------|--|
| AE           | adverse event                                  |
| ATC          | anatomical therapeutic class                   |
| BLQ          | below limit of quantification                  |
| BMI          | body mass index                                |
| BSA          | body surface area                              |
| CBR          | clinical benefit rate                          |
| CMQ          | customized MedDRA queries                      |
| CR           | complete response                              |
| CRF          | case report form                               |
| CSAEs        | clinically significant adverse events          |
| CTCAE        | Common Terminology Criteria for Adverse Events |
| DCR          | disease control rate                           |
| DOR          | duration of response                           |
| DBP          | diastolic blood pressure                       |
| EMA          | European Medicines Agency                      |
| HRQoL        | Health-Related Quality of Life                 |
| IIR          | independent imaging review                     |
| IRT          | interactive response technology                |
| ITT          | intent-to-treat                                |
| K-M          | Kaplan-Meier                                   |
| KPS          | Karnofsky performance status                   |
| LLT          | lower level term                               |
| LVEF         | left ventricular ejection fraction             |
| MedDRA       | Medical Dictionary for Regulatory Activities   |
| NA           | not applicable                                 |
| NE           | not evaluable                                  |
| ORR          | objective response rate                        |
| OS           | overall survival                               |
| OS-1y        | overall survival rate at 1 year                |

| Abbreviation | Term   |
|---------------------|---|
| PD                  | pharmacodynamic(s) or progressive disease/disease progression |
| PedsQL              | Pediatric Quality of Life Inventory                           |
| PFS                 | progression-free survival                                     |
| PFS-4m              | progression-free survival rate at 4 months                    |
| PFS-1y              | progression-free survival rate at 1 year                      |
| PK                  | pharmacokinetic(s)  |
| PR                  | partial response  |
| PRO                 | patient-reported outcome                                      |
| PT                  | preferred term  |
| QTc                 | corrected QT interval   |
| QTcB                | corrected QT interval using Bazett's correction factor        |
| QTcF                | corrected QT interval using Fridericia's correction factor    |
| RECIST              | Response Evaluation Criteria in Solid Tumors                  |
| SAE                 | serious adverse event   |
| SAP                 | statistical analysis plan                                     |
| SBP                 | systolic blood pressure                                       |
| SD                  | standard deviation or stable disease                          |
| SI                  | Système International   |
| SMQs                | standardized MedDRA queries                                   |
| SOC                 | system organ class  |
| TEAE                | treatment-emergent adverse event                              |
| TLG                 | tables, listings, and graphs                                  |
| TNM                 | tumor-node-metastasis   |
| TSH                 | thyroid stimulating hormone                                   |
| WHO DD              | World Health Organization Drug Dictionary                     |

## 4 INTRODUCTION

The purpose of this statistical analysis plan (SAP) is to describe the procedures and the statistical methods that will be used to analyze and report results of the primary analysis for Eisai Protocol E7080-G000-230 Amendment 02. Analyses on subjects' Health-Related Quality of Life (HRQoL) data, pharmacokinetic (PK)/pharmacodynamics (PD), biomarkers, and relationships between PK and efficacy/safety will be included in separate statistical analysis plans.

### 4.1 Study Objectives

#### 4.1.1 Primary Objective

To evaluate whether lenvatinib in combination with ifosfamide and etoposide (Arm A) is superior to ifosfamide and etoposide (Arm B) in improving progression-free survival (PFS) by independent imaging review (IIR) using Response Evaluation Criteria In Solid Tumors (RECIST 1.1 [Eisenhauer, et al., 2009]), in children, adolescents, and young adults with relapsed or refractory osteosarcoma.

#### 4.1.2 Secondary Objectives

The secondary objectives of the study are to:

1. Compare difference in PFS rate at 4 months (PFS-4m) between the 2 treatment arms per IIR
2. Compare difference in PFS rate at 1 year (PFS-1y) between the 2 treatment arms per IIR
3. Compare differences in overall survival (OS) and OS rate at 1 year (OS-1y) between the 2 treatment arms
4. Compare difference in objective response rate (ORR) at 4 months (ORR-4m) between the 2 treatment arms per IIR
5. Compare difference in objective response rate (ORR) between the 2 treatment arms per IIR
6. Compare differences in safety and tolerability between the 2 treatment arms
7. Characterize the PK of lenvatinib, when administered in combination with ifosfamide and etoposide
8. Compare differences in HRQoL as assessed by using the Pediatric Quality of Life Inventory (PedsQL) Generic Core Scales and Cancer Module between the 2 treatment arms
9. Assess the palatability and acceptability of the suspension formulation of lenvatinib in subjects receiving the suspension formulation in the study

#### 4.1.3 Exploratory Objectives

The exploratory objectives of the study are to:

1. Explore differences in duration of response (DOR), disease control rate (DCR), and clinical benefit rate (CBR) between the 2 treatment arms per IIR and investigator assessment+
2. Explore differences in PFS, PFS-4m, PFS-1y, ORR-4m, and ORR between the 2 treatment arms per investigator assessment
3. Compare between the 2 treatment arms:
  - the proportion of subjects who achieve complete removal of baseline lesion(s)
  - the proportion of subjects with unresectable baseline lesion(s) that are converted to resectable
4. Investigate the relationship between subject tumor biomarkers and clinical response and toxicity of lenvatinib in combination with ifosfamide and etoposide

## 4.2 Overall Study Design and Plan

This is a multicenter, randomized, open-label, parallel-group, Phase 2 study to compare the efficacy and safety of lenvatinib in combination with ifosfamide and etoposide versus ifosfamide and etoposide in children, adolescents, and young adults with relapsed or refractory osteosarcoma.

Approximately 72 eligible subjects will be randomized to 1 of the following 2 treatment arms in a 1:1 ratio within the strata:

- Arm A: lenvatinib 14 mg/m^2 (orally, once daily) plus ifosfamide 3000 mg/m^2/day (intravenously [IV], Day 1 to Day 3 of each cycle for a total of up to 5 cycles) and etoposide 100 mg/m^2/day (IV, Day 1 to Day 3 of each cycle for a total of up to 5 cycles)
- Arm B: ifosfamide 3000 mg/m^2/day (IV, Day 1 to Day 3 of each cycle for a total of up to 5 cycles) and etoposide 100 mg/m^2/day (IV, Day 1 to Day 3 of each cycle for a total of up to 5 cycles)

Randomization will follow a predefined randomization scheme based on the following stratification factors: time to first relapse/refractory disease (early [ $<18$  months] or late [ $\geq 18$  months]) and age ( $<18$  and  $\geq 18$  years).

Eisai will closely monitor enrolment, to ensure that at least 36 subjects are  $<17$  years of age at the time of informed consent per regulatory requirement.

The study will be conducted in 3 Phases: a Prerandomization Phase, a Randomization Phase, and an Extension Phase.

The end of the study will be the date of data cutoff for the final analysis or the time of last subject last visit, whichever occurs later.

An overview of the study design is presented in Figure 1 in the Protocol.

#### 4.2.1 Prerandomization Phase

The Prerandomization Phase will consist of 2 periods: Screening and Baseline. The Prerandomization Phase will last no longer than 28 days. The Screening Period will establish protocol eligibility and the Baseline Period will confirm eligibility.

##### 4.2.1.1 Screening Period

Screening will occur between Day -28 and Day -2. The purpose of the Screening Period is to obtain informed consent and to establish protocol eligibility. Informed consent will be obtained after the study has been fully explained to each subject and before the conduct of any screening procedures or assessments. Procedures to be followed when obtaining informed consent are detailed in Section 5.3 of the Protocol.

Subjects must have a histologically or cytologically confirmed diagnosis of high grade refractory or relapsed osteosarcoma as detailed in the Inclusion Criteria (Section 9.3.1 of the Protocol).

The Screening Disposition case report form (CRF) page must be completed to indicate whether the subject is eligible to participate in the study and to provide reasons for screen failure, if applicable.

##### 4.2.1.2 Baseline Period

The purpose of the Baseline Period is to confirm protocol eligibility as specified in the inclusion/exclusion criteria (as detailed in Section 9.3.1 and Section 9.3.2 of the Protocol). Results of baseline assessments must be obtained prior to the first dose of study drug (Cycle 1 Day 1). Baseline assessments may be performed on Day -1 or on Cycle 1 Day 1 prior to dosing. Clinical laboratory tests (Table 4 of the Protocol), including a pregnancy test (where applicable), should be performed within 72 hours prior to the first dose of study drug.

Subjects who complete the Baseline Period and continue to meet the criteria for inclusion/exclusion (as detailed in Section 9.3.1 and Section 9.3.2 of the Protocol) will begin the Randomization Phase of this study.

#### 4.2.2 Randomization Phase

The Randomization Phase will consist of 2 periods: Treatment Period and Follow-up Period. The Randomization Phase will begin at the time of randomization of the first subject and will end on the data cutoff date for the primary analysis (ie, when approximately 38 PFS events, as determined by IIR, are observed).

After the data cutoff date for the primary analysis has occurred, all subjects who are still on study treatment will enter the Extension Phase.

#### 4.2.2.1 Treatment Period

The Treatment Period for each subject will begin at the time of randomization and will end at the completion of the Off-Treatment Visit which will occur within 30 days after the final dose of study treatment.

Subjects will receive study treatment as continuous 21-day cycles in both treatment arms. Treatment cycles will be counted continuously regardless of dose interruptions. If chemotherapy administration is precluded on Day 1 of a treatment cycle, the subject may resume treatment once recovered at the discretion of the investigator. Subsequent chemotherapy will be administered every 21 ( $\pm 1$ ) days starting from the timepoint it was resumed. Subjects will undergo safety and efficacy assessments as defined in the Schedule of Procedures/Assessments (Table 5 of the Protocol). Subjects randomized to Arm A will continue to receive lenvatinib until disease progression (PD) confirmed by IIR, development of unacceptable toxicity, subject request, withdrawal of consent, or study termination by the sponsor, whichever occurs first.

Disease progression (PD) must be confirmed by IIR prior to the investigator discontinuing study treatment for a subject. In situations where the investigator judges that alternative treatments must be instituted immediately for a subject's safety, study drugs may be discontinued without waiting for IIR confirmation of radiographic evidence of PD. If possible, before discontinuation of the subject from the study, the investigator should consult with the sponsor.

#### 4.2.2.2 Follow-up Period

The Follow-up Period begins the day after the Off-Treatment Visit and will continue for up to 2 years after end of treatment for a subject, unless the subject withdraws consent, or is lost to follow-up, or the sponsor terminates the study.

Subjects may at any time withdraw consent for further study participation. No further data will be collected on subjects once consent has been withdrawn; however, an investigator may consult public records to establish survival status if permitted by local regulations.

All adverse events (AEs), including serious adverse events (SAEs), will be captured for 30 days after the last dose of study drug.

All subjects who end study treatment without IIR confirmed PD will continue to undergo tumor assessments every 6 weeks until Week 18, then every 9 weeks until Week 54, thereafter, every 12 weeks until IIR confirmation of radiographic evidence of PD as described in the tumor assessments in the assessment schedule, or until another anticancer therapy is initiated.

Subjects in both Arm A and Arm B will be followed for survival every 12 weeks ( $\pm 1$  week) and all subsequent anticancer treatments received will be recorded. Subjects who are being

followed for survival at the primary analysis (ie, at the end of the Randomization Phase) will continue to be followed for survival during the Follow-up Period of the Extension Phase.

#### 4.2.3 Extension Phase

The Extension Phase starts after completion of the Randomization Phase (data cutoff for primary analysis). The Extension Phase will consist of 2 periods: Treatment Period and Follow-up Period.

##### 4.2.3.1 Treatment Period

In the Treatment Period, subjects still on study treatment following the completion of the Randomization Phase will continue study treatment as outlined in Protocol Section 9.4.1 until disease progression, development of unacceptable toxicity, subject request, withdrawal of consent, or discontinuation of study by the sponsor. Tumor assessments will be performed according to the local standard of care. Independent imaging review (IIR) and confirmation of radiographic evidence of PD will not be required, and scans will no longer be required to be sent to the imaging core laboratory. The Off-Treatment Visit will occur within 30 days after the final dose of study treatment. All AEs, including SAEs will be captured up to 30 days after last dose of study drug. In case the study is discontinued by the sponsor, the sponsor will continue to provide study drug (outside the study) for subjects who have not met the criteria for study drug discontinuation.

##### 4.2.3.2 Follow-Up Period

The Follow-up Period will begin the day after the Off-Treatment Visit and will last for up to 2 years after end of treatment for a subject, unless the study is terminated by the sponsor, or the subject discontinues due to withdrawal of consent, or is lost to follow-up. Subjects will be treated by the investigator according to the prevailing local standard of care. Subjects will be followed every 12 weeks ( $\pm 1$  week) for survival and all subsequent anticancer treatments received will be recorded.

#### 4.2.4 Optional Lenvatinib Crossover (for Subjects in Arm B Only)

Subjects in Arm B with disease progression per RECIST 1.1 may be eligible for optional treatment with lenvatinib alone (after 5 cycles of chemotherapy) or lenvatinib plus chemotherapy (before 5 cycles of chemotherapy). Note: subjects may only receive a maximum of 5 cycles of chemotherapy for the duration of the study. Optional Lenvatinib crossover treatment must be initiated within 30 days of documented disease progression.

Optional lenvatinib crossover treatment is only available if the following conditions are met:

- Subject experiences disease progression per RECIST 1.1 (as confirmed by IIR for all subjects who cross over prior to the start of the Extension Phase); and
- No new systemic anticancer medication was administered after the last dose of study drugs; and
- The subject meets all of the safety parameters listed in the inclusion criteria and none of the safety parameters listed in the exclusion criteria; and

- The study is ongoing.

Treatment with lenvatinib alone or lenvatinib plus chemotherapy will continue until the next disease progression (per RECIST 1.1 as assessed by investigator only), development of unacceptable toxicity, subject request, or withdrawal of consent, whichever occurs first.

Prior to optional lenvatinib crossover treatment, baseline tumor assessment must be re-established (ie, new tumor assessment scans performed), unless the last tumor assessment scans were performed within 4 weeks prior to Cycle 1 Day 1 of the crossover treatment.

Subjects who qualify to receive optional lenvatinib crossover treatment will be followed according to the schedule of procedures/assessments in Table 7 of the Protocol.

## 5 DETERMINATION OF SAMPLE SIZE

A total sample size of 72 subjects is estimated for the primary efficacy endpoint of PFS. A median PFS of 3.5 months for Arm B (control arm) has been assumed by comparing available PFS data from clinically active agents in this patient population (Davis, et al., 2019; Palmerini, et al., 2016; Grignani, et al., 2012). With respect to Arm A (lenvatinib plus chemotherapy arm), a median PFS of 8.75 months is assumed based on the results from Study E7080-G000-207.

Therefore, assuming a hazard ratio of 0.4, a 1-sided type 1 error rate of 0.025, and power of 80%, the required number of PFS events for the study is 38. The primary PFS analysis is estimated to occur at approximately 32 months after the first subject is randomized (assuming a 20-month enrollment period), and accounts for an overall dropout rate of up to 40%. This dropout rate includes the potential early dropouts and subjects who are censored before the data cutoff.

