### 6.3.2 Adjustments for Covariates

The stratified log-rank test for the primary efficacy endpoint, PFS as assessed by IIR, the secondary efficacy endpoint, OS, the stratified Miettinen and Nurminen's method for the secondary efficacy endpoint of ORR, and the stratified Cox regression analyses to estimate

hazard ratios (time-to-event efficacy endpoints) will be performed using the following randomization stratification factors from IRT.

- Time to first relapse/refractory disease (early [ $<18$  months] or late [ $\geq 18$  months])
- Age ( $<18$  and  $\geq 18$  years)

In case of low numbers of subjects enrolled within any combination of stratification factors, subjects from the low enrollment combination(s) of the stratification factors may be pooled for analysis.

Based on a blinded review of the data, the number of subjects in the level of the stratum “time to first relapse/refractory disease  $\geq 18$  months” is approximately 11 subjects out of 81 subjects in the ITT population. To ensure a sufficient number of participants in each stratum within each treatment arm, “time to first relapse/refractory disease” has been removed as a stratification factor in the analyses. Thus, only the stratification factor “age at randomization” will be included in any stratified analyses.

Other demographic and baseline variables may be included and adjusted in the statistical models as sensitivity analyses if deemed necessary.

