### 6.4.1 Primary Efficacy Analysis

The primary efficacy endpoint of PFS per IIR will be analyzed and compared between the 2 treatment arms by the stratified log-rank test adjusted for the randomization stratification factor (refer to [Section 6.3.2](#)). Median PFS will be calculated using the K-M product-limit estimates for each treatment arm along with 2-sided 95% CIs (estimated with a generalized Brookmeyer and Crowley method [[Brookmeyer and Crowley, 1982](#)]). The K-M estimates of PFS will be plotted over time. The stratified Cox regression model will be used to estimate the hazard ratio and its 95% CI.

The PFS by IIR is defined as the time from the date of randomization to the date of first documentation of disease progression based on IIR assessments using RECIST 1.1 or date of death, whichever occurs first.

Determination of the date of PFS event or censoring is summarized in Table 2 below. The table is based on the FDA clinical trial endpoints guidance of 2007 (FDA, 2007). In this study, removal of baseline lesion(s) is permitted after completion of the Week 18 tumor assessment, and palliative radiotherapy of non-target lesions is allowed (see protocol 9.4.7.3). For the primary efficacy endpoint analysis, PFS will be censored according to censoring rules in Table 2. In this analysis, assessments after removal of baseline lesion(s) (considered as a new anticancer therapy) before or after Week 18 will be censored.

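### The 80% power stated for 38 PFS events is slightly optimistic: the planned age-stratified log-rank test has about 77% at a hazard ratio of 0.4

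*SAP*

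**What the plan says.** SAP Section 5 builds the design as follows:

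- Control arm: "A median PFS of 3.5 months for Arm B (control arm) has been assumed".
- Experimental arm: "a median PFS of 8.75 months is assumed based on the results from Study E7080-G000-207".
- Effect and error rate: "assuming a hazard ratio of 0.4" and "a 1-sided type 1 error rate of 0.025".
- Result: "power of 80%, the required number of PFS events for the study is 38".
- Size: "A total sample size of 72 subjects is estimated for the primary efficacy endpoint of PFS", with 20 months of enrolment, analysis at about 32 months, and overall dropout of up to 40%.

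Section 5 names neither the formula used nor any simulation.

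Section 6.4.1 compares the arms "by the stratified log-rank test adjusted for the randomization stratification factor". Section 6.3.2 reduces the strata to age alone (under 18 versus 18 and over) after a blinded review found that the late-relapse level held "approximately 11 subjects out of 81 subjects in the ITT population". Sections 4.2.2 and 6.4 place the primary analysis at an approximate count of 38 PFS events by independent imaging review.

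**The concern.** The usual event formula for a log-rank test is a local approximation. It is accurate when the hazard ratio is near 1, and it treats subjects at risk as evenly split between the arms throughout. At a hazard ratio of 0.4 the control arm empties much faster. Later events then fall in risk sets dominated by Arm A and carry less information than the formula credits. The planned test is also stratified, which usually costs a little power when the strata are small.

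There is one primary test and no interim analysis (Section 7), so power at 38 events is the design's main operating characteristic. If it is below 80%, a non-significant result is somewhat less informative about the assumed effect than Section 5 implies.

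**Working it through.** **Inputs from the SAP.** Hazard ratio 0.4 (3.5/8.75 = 0.40, consistent with exponential PFS); 1-sided alpha 0.025 (z = 1.960); power 80% (z = 0.8416); 1:1 allocation; 72 planned and 81 randomized subjects; 20-month accrual; log-rank test stratified by age.

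**Inputs assumed, not in the SAP.** Share of subjects under 18 (50%, 55% or 67%), permuted blocks of 4 within age strata, uniform accrual, exponential dropout, and in some runs a prognostic age effect.

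**Step 1: reproduce the plan's figure (Schoenfeld).**

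- Events = 4 × (1.960 + 0.8416)² / (ln 0.4)² = 4 × 7.849 / 0.8396 = 37.4, rounded up to 38.
- Power at 38 = Φ(√38 × 0.9163 / 2 − 1.960) = Φ(0.864) = 80.6%.

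The figure reproduces.

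**Step 2: a second approximation, as a bracket (Freedman).**

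- Events = (1.4/0.6)² × 7.849 = 42.7, rounded up to 43.
- Power at 38 = Φ(√38 × 0.6/1.4 − 1.960) = Φ(0.682) = 75.2%.

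The two formulas differ by about 5 points at 38 events, so simulation has to decide between them.

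**Step 3: simulate the planned test.** Exponential PFS with the SAP's medians, cutoff at the 38th event, 20,000 trials per scenario (standard error about 0.3 points):

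| Subjects | Dropout per month | Share <18 | Unstratified | Age-stratified |
|---|---|---|---|---|
| 72 | 0 | 50% | 78.4% | 77.1% |
| 72 | 0 | 67% | 79.2% | 77.7% |
| 72 | 3% | 50% | 78.3% | 77.2% |
| 72 | 3% | 67% | 78.6% | 77.4% |
| 72 | 6% | 50% | 78.5% | 77.1% |
| 72 | 6% | 67% | 78.2% | 76.7% |
| 81 | 0 | 50% | 79.3% | 78.3% |
| 81 | 0 | 67% | 78.6% | 77.3% |
| 81 | 3% | 50% | 79.1% | 77.8% |
| 81 | 3% | 67% | 78.1% | 77.2% |
| 81 | 6% | 50% | 78.0% | 76.6% |
| 81 | 6% | 67% | 78.3% | 76.7% |

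The averages are 78.5% unstratified and 77.3% stratified.

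**Step 4: split the loss.** From Schoenfeld's 80.6% to the unstratified 78.5% is about 2.1 points, due to the large-effect approximation. From 78.5% to 77.3% is about 1.3 points, due to stratification.

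**Step 5: robustness** (72 subjects, 55% under 18, 12,000 trials each, standard error about 0.4 points). Stratified power at 38 events:

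- No dropout: 76.6%.
- 5% dropout per month, with progression read only on the 6/9/12-week scan schedule: 76.6%.
- Age prognostic with hazard ratio 1.5: 76.2% with no dropout, 76.3% with the scan schedule and 5% dropout.
- Under no effect, the stratified test rejects in 2.6% of trials, in line with 2.5%. The shortfall is therefore not caused by a conservative test.

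**Step 6: timing.** In Step 3 the 38th event arrives at about 16 to 21 months, earlier than the SAP's 32. Fixing the cutoff at 32 months and raising dropout to 10% per month gives 39.1 events on average and 77.8% stratified power. With 9% dropout it is 40.8 events and 79.7%. Power follows the event count, and the heavier dropout implied by 32 months does not change the picture.

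**The case against.** The strongest reply is that nothing is miscalculated. Schoenfeld's formula is standard, 38 follows from it, and choosing Freedman's formula or simulation instead is a preference about method. The gap is about 3 points, the trigger is only approximate, about 41 events would restore 80%, and the uncertainty in the two assumed medians is far larger. The test, the estimand and the type I error are untouched.

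Most of this stands, and it keeps the point minor. It does not remove it: Section 5 gives 80% as the power of the design, and the design's own test does not quite reach it in any age split, dropout rate or sample size simulated at 38 events.

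A reader might infer more than the SAP supports:

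- *That 38 is an arithmetic error.* It is not (Step 1).
- *That power is as low as 75%, or that 43 events are needed.* Those figures are Freedman's approximation, which errs in the other direction here. Simulated values near 75% arose only under extreme loss. With 72 subjects and 9% dropout per month, power was 75.3-76.4%, but 16% of those trials never reached 38 events, so this is not power at 38. If 40% of subjects contribute nothing, two simulations gave 75.1% and 76.2%.
- *That age stratification is the main cause.* It accounts for the smaller part, and the unstratified test also falls short of 80%.
- *That the trigger should simply move to about 42 events.* That count ends the Randomization Phase (Section 4.2.2) and, with it, the requirement for independent imaging review (Section 4.2.3.1), in an open-label trial with 81 subjects already randomized. The delay is also uncertain: with 81 subjects, about 1.6 months under 6% monthly dropout (18.9 to 20.5), but about 4 months if 40% contribute nothing (24.2 to 28.4).

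**Conclusion.** The point holds as a minor one. At exactly 38 events and a hazard ratio of 0.4, the planned age-stratified log-rank test has simulated power of about 77% (range about 76-78%), against the stated 80%. The type II error is about 23% rather than 20%. The gap is several times the simulation error.

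The conclusion rests on exponential PFS with the SAP's medians, and on assumed age shares of 50-67% under 18, blocks of 4 and dropout of 0-6% per month. It changes little across those choices. It affects how the design is described and how a non-significant result would be read; it does not affect the validity of the primary analysis.

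**What to change.** In Section 5, name the formula behind the 38 events (the figure matches Schoenfeld's) and add that simulation of the planned age-stratified log-rank test at 38 events, under the stated assumptions, gives power of about 77%. State the simulation inputs that the SAP does not otherwise give: age split, block size and dropout pattern. Leave the 38-event trigger unchanged.

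The cost is one sentence and a slightly less favourable stated figure. No analysis, timing or subject number changes.
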